
Treatment Period: Dosing D1 through W16
	
 • AEs: at each visit query subject about any such AEs • Concomitant medications and treatments: at each visit query subject about any new medications or treatments

	
 • Check prior and current injection site at each visit prior to release from the clinic • Safety labs per Schedule of Events (Table 1) and at ET, if applicable • Trough PK levels and PD assessments per Schedule of Events (Table 1) and at ET, if applicable • ADA per Schedule of Events (Table 1) and at ET, if applicable • Efficacy and PROs assessments: per Schedule of Events (Table 1) and at ET, if applicable. Note that PP-NRS score of the maximal itch intensity over the previous 24 hours will be documented in the subject diary for each day, including the visit day. • Administer study drug and monitor vital signs (VS) • Ensure that clinic discharge criteria are met and review with the subject study requirements and date/time for the next visit

Follow Up Period: W17-W24
	
 • AEs: at each visit query subject about any AEs • Concomitant medications and treatments: at each visit query subject about any new medications or treatments • Check prior injection sites • Efficacy and PROs assessments: per Schedule of Events (Table 1) and at ET, if applicable. Note that PP-NRS score of the maximal itch intensity over the previous 24 hours will be documented in the subject diary for each day, including the visit day. • Safety labs and ECG: W24 • Trough PK, PD and ADA sampling per Schedule of Events (Table 1) • Review with the subject study requirements and date/time for the next visit

Efficacy Outcome Measures:
	
Per Schedule of Events (Table 1) and at ET, if applicable:
 
 • Investigator: IGA, EASI, BSA, SCORAD • Patient-reported outcomes: PP NRS, DLQI, POEM

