Study subjects are adults between 18 and 75 years old (both included) at the screening visit (Screening) with AD (according to American Academy of Dermatology Consensus Criteria, Eichenfield 2014) present for at least 1 year prior to the baseline visit (Baseline). In terms of AD, subjects must have an inadequate response to AD treatment with a topical regimen of corticosteroids, phosphodiesterase inhibitors or calcineurin inhibitors, or for whom topical treatments are otherwise medically inadvisable, and have IGA score ≥ 3 , EASI score ≥ 16 , and BSA for total AD involvement $\geq 10\%$ at Screening and Baseline.

C. Sample Size Determination

A sample size of 220 (55 per arm, providing approximately 44 completers per treatment group assuming 20% dropout rate) will provide 95% power to detect at treatment effect on the primary endpoint of percentage reduction of EASI at week 16 between the CBP-201 300 mg Q2W vs. Placebo. This power calculation

is based on the use of a two-sided two-sample t test at the $\alpha=0.05$ level of significance. Based on the preliminary results at Week 4 and empirical data, the mean between-group difference is assumed to be equal to 35 percentage points and the pooled standard deviation is assumed to be 45% using 2-sample independent t-test.

D. Treatment Randomization

Patients will be randomized at a 1:1:1:1 ratio into the following 4 groups: CBP-201 1800 mg (600mg load D1 then 150 mg Q2W), CBP-201 3000 mg dose (600mg load D1 then 300 mg Q2W), CBP-201 1800 mg dose (600mg load D1 then 300 mg Q4W), or placebo, respectively. The randomization is not stratified.

E. Assessment Schedule

The date at which the subject is randomized will be referred to as the “Baseline/Day 1” visit. Subjects will be requested to attend the scheduled visits for the Treatment Period every 2 weeks from their Baseline/Day 1 visit through Week 16. The acceptable visit window for scheduled visits during the Treatment Period is ± 2 days. After Week 16 of treatment, subjects will no longer receive any treatments but will return for an additional 8 weeks for follow-up visits. The acceptable visit window for scheduled visits during the Follow-up Period is ± 3 days.

In the case of an early termination (ET) from the study for any reason, study completion assessments should be performed as detailed for the study completion visit and should be completed within 7 days of the ET, whenever possible.

F. Clinical Trial Material

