CBP-201 is provided as a single-use 2 mL vial containing 1.2 mL clear to slightly yellow sterile solution. Placebo is provided as a single-use 2 mL vial containing 1.2 mL solution without CBP-201 and is identical in appearance. The protocol provides additional product details in Section 9.

5. General Analytical Considerations

A. Data Sources and General Rules

Data are recorded on electronic case report form (eCRF) for each subject screened/enrolled in this study. These forms will be used to transmit information collected during the study to the Sponsor and regulatory authorities, as applicable. Laboratory data, ECG and blood samples data are collected separately by the selected vendors. Section 12 of the protocol provides additional details regarding data handling and record keeping.

Statistical analysis will be performed following IQVIA Biotech standard operating procedures and on the IQVIA Biotech computer network. All statistical analysis will be performed using SAS Version 9.4 or higher with program code prepared specifically for the project by qualified IQVIA Biotech statisticians and SAS programmers.

All continuous study assessments will be summarized by treatment and time point (as applicable) using the descriptive statistics n, mean, standard deviation (SD), median, and range (minimum, and maximum). Categorical assessments will be summarized by treatment and time point (as applicable) using frequency counts and rates of occurrence (%). The formal statistical comparison will be performed on the primary efficacy endpoints only, while descriptive statistics, together with Clopper-Pearson exact confidence interval (CI) for proportions, will be provided. All statistical tests will be conducted using 2-sided tests with 5% Type 1 error rates unless otherwise stated.

B. Definition of Baseline and Study Day

Baseline is defined as the last non-missing assessment prior to the date of the first administration of study treatment. In particular, the PP-NRS assessment will be collected once daily based on peak pruritus over the last 24 hours. The baseline PP-NRS will be defined as the mean value of all entries (at least 4 entries) during last week preceding randomization from Day -7 to Day -1. If a subject missed more than 3 entries during the 7 days before Baseline visit, the baseline PP-NRS value will be considered as undefined (missing) for the subject.

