Reduction from baseline will be defined as: $\text{Baseline value} - \text{post-Baseline value}$. The percent reduction from Baseline will be calculated as reduction from Baseline divided by the Baseline value, expressed as a percentage.

Change from Baseline is defined as: $\text{post-Baseline value} - \text{Baseline value}$. The percent change from Baseline will be calculated as change from Baseline divided by the Baseline value, expressed as a percentage.

Day 1 is defined as the date of first administration of study treatment. Study day is calculated relative to the date of Day 1.

C. Analysis Visit Window

Because all study medication will be administered at the study center via subcutaneous (SC) injection every 2 weeks, all efficacy and safety endpoints will be summarized and analyzed according to their nominal visit as assigned, except for ET visits. ET visits will be re-mapped to the last nominal visit number + 1. For example, if a subject attended Week 2, Week 4, Week 6 and then early terminated, the early termination visit will be re-mapped and analyzed as Week 8. No analysis visit window mapping based on actual study day will be performed other than that for ET visits.

Unscheduled visits will not be re-mapped and will not be included in table summaries. They will only be listed.

D. Multiple Study Centers

This study will be conducted by multiple investigators at multiple centers internationally. Descriptive summaries of the primary and secondary efficacy endpoints will be presented for each individual study center to evaluate potential heterogeneity across sites. Baseline characteristics and key safety endpoint may be presented for each study center as appropriate. The implications of any significant heterogeneity on the assessment of overall efficacy will be explored.

E. Covariate Adjustment in Primary Analysis

The primary efficacy analyses will adjust for baseline EASI score and baseline IGA score (moderate, severe) as described in Section 8 Efficacy Analyses below.

F. Subgroup Analysis

Exploratory subgroup analysis of the primary or other efficacy endpoints based on demographic factors or other covariates may be performed on an ad hoc basis, using descriptive statistics. Grouping factors may include:

- Age
- Sex
- Race
- Ethnicity
- Baseline IGA Score

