 - **For Treatment Period:** Baseline (Day -7 to -1), Week 1 (Day 1 to 7), Week 2 (Day 8 to 14), Week 3 (Day 15 to 21), Week 4 (Day 22 to 28), etc., until Week 16 (Day 106 + for subjects not enrolled into Follow-up Period, Day 106 to Day of Week 16 visit for subjects enrolled into Follow-up Period).
 - **For Follow-up Period:** Week 17 (Day of Week 16 visit +1 to Day 119), Week 18 (Day 120 to 126), etc., until Week 24 (Day 162 to End of Study Visit).
 - Subjects must complete at least 4 NRS entries to calculate the weekly average. The weekly average will be considered missing if more than 3 entries are missing for that weekly interval.
- **POEM** is a 7-item questionnaire assessing disease symptoms on a 0 to 4 scale (dryness, itching, flaking, cracking, sleep loss, bleeding and weeping) with a scoring system of 0 (absent disease) to 28 (severe disease); higher scores indicative of poorer quality of life.
- **DLQI** is 10-item questionnaire assessing the impact of AD on quality of life (QOL) over the past week, with an overall scoring of 0 (absent disease) to 30 (severe disease); higher scores indicative of poorer QOL.

The scoring of each question is as follows:

Response	Score
Very much	scored 3
A lot	scored 2
A little	scored 1
Not at all	scored 0
Not relevant	scored 0
Question unanswered	scored 0
Question 7: “prevented work or studying”	scored 3

The scoring of DLQI will follow the developer's manual². Specifically:

- If one question is left unanswered this is scored 0 and the scores are summed and expressed as usual out of a maximum of 30.
- If two or more questions are left unanswered the questionnaire is not scored.
- If question 7 is answered 'yes' this is scored 3. If question 7 is answered 'no' but then either 'a lot' or 'a little' is ticked this is then scored 2 or 1. If "Not relevant" is ticked, the score for Question 7 is 0. If it is answered 'no', but the second half is left incomplete, the score will remain 0.
- If two or more response options are ticked, the response option with the highest score should be recorded.
- If there is a response between two tick boxes, the lower of the two score options should be recorded.

B. Primary Efficacy Outcome Analysis

The primary efficacy endpoint will be comparing percentage reduction in EASI from baseline to Week 16 for each CBP-201 regimen versus placebo.

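### The Week 16 PP-NRS interval runs 6 to 10 days, but its completeness rules fit only a 7-day week, so the number of diary entries required depends on the visit date

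*SAP*

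**What the plan says.** SAP section 8.A (PP-NRS) sets out the diary weeks. Baseline is Day -7 to Day -1, and Weeks 1 to 15 are consecutive 7-day blocks. Week 16 is defined differently for two groups: "Day 106 to Day of Week 16 visit for subjects enrolled into Follow-up Period", and "Day 106 + for subjects not enrolled into Follow-up Period". The second definition gives no last day.

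Two completeness rules then apply to every interval, whatever its length: "Subjects must complete at least 4 NRS entries to calculate the weekly average", and "The weekly average will be considered missing if more than 3 entries are missing for that weekly interval". For baseline, SAP section 5.B ties the missing-entry rule to a stated length: "If a subject missed more than 3 entries during the 7 days before Baseline visit", the baseline value is undefined.

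Three other statements fix the length of the Week 16 interval:

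- SAP section 5.B: "Day 1 is defined as the date of first administration of study treatment".
- SAP section 4.E: "The acceptable visit window for scheduled visits during the Treatment Period is" ±2 days. Protocol Table 1 puts the Week 16 visit at Day 113.
- Protocol synopsis: the itch score is "documented in the subject diary for each day, including the visit day", so the visit day can supply an entry.

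The Week 16 change in weekly average PP-NRS is a secondary endpoint (SAP section 3.B). The proportions with at least a 3-point and at least a 4-point reduction are other efficacy endpoints (SAP section 3.C). Under SAP section 5.J, a missing value is carried forward from the last post-baseline observation for the change endpoint and counted as non-response for the responder endpoints.

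**The concern.** A minimum of 4 present and a maximum of 3 missing are the same condition only when 7 entries are possible. Week 16 is the time point that matters most for itch, and it is the one week of the treatment period whose length is not fixed at 7 days. Even a subject who attends exactly on schedule has an 8-day interval.

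The completeness standard at Week 16 therefore depends on which day the subject came in. Most subjects seen on or after the scheduled day face a higher count than they did at baseline or in any earlier week. The outcome decides whether the observed Week 16 average is used or replaced, by LOCF for the change endpoint and by non-response for the 3- and 4-point endpoints. The SAP gives no reason for this dependence on visit timing and does not say how the two rules combine.

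For the group with the open-ended interval, the number of entries expected is undefined. The count of missing entries therefore cannot be computed at all.

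**Working it through.** **Reference case.** For a 7-day interval (baseline and Weeks 1 to 15), the first rule needs k ≥ 4 entries and the second needs 7 − k ≤ 3, which is also k ≥ 4. The rules agree for every k.

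**Length of Week 16.** L = visit day − 106 + 1, with the visit on Day 113 ±2.

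**Minimum entries.** Rule A: k ≥ 4. Rule B: L − k ≤ 3, so k ≥ L − 3. Applied together: k ≥ max(4, L − 3).

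| Visit day | L | Rule A | Rule B | Both | Counts where the rules differ |
|---|---|---|---|---|---|
| 111 | 6 | 4 | 3 | 4 | 3 |
| 112 | 7 | 4 | 4 | 4 | none |
| 113 (on schedule) | 8 | 4 | 5 | 5 | 4 |
| 114 | 9 | 4 | 6 | 6 | 4, 5 |
| 115 | 10 | 4 | 7 | 7 | 4, 5, 6 |

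The rules coincide only for a visit one day early. SAP section 5.C analyses by nominal visit, so a visit later than Day 115 would lengthen the interval further.

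**Share of subjects between the rules.** The documents give no diary completion rate. Assume each day is completed independently with probability p. For the 8-day window the share is P(k = 4) = 70 × p⁴ × (1 − p)⁴:

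- p = 0.9: 70 × 0.6561 × 0.0001 = 0.5%
- p = 0.8: 70 × 0.4096 × 0.0016 = 4.6%
- p = 0.7: 70 × 0.2401 × 0.0081 = 13.6%

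Summing the binomial terms over the differing counts gives, at p = 0.8, 8.2%, 0%, 4.6%, 8.3% and 12.0% for visits on Days 111 to 115. If visits are spread evenly over those five days, the mean is (8.2 + 0 + 4.6 + 8.3 + 12.0) / 5 = 6.6%. With the 44 completers per arm that the plan assumes, this is 0.066 × 44 ≈ 2.9 subjects per arm. If every visit is on schedule it is 0.046 × 44 ≈ 2.0.

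**Other intervals.** Week 17 runs from the day after the Week 16 visit to Day 119, so it has 4 to 8 days. Week 24 runs from Day 162 to the end-of-study visit (Day 169 ±3), so it has 5 to 11 days. Week 20 is Days 134–140, exactly 7, so the Week 20 itch endpoints are not affected.

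**The case against.** A reader might infer that the two rules contradict each other, so that one diary yields both a valid mean and a missing value. The text does not support that. The first rule states a necessary condition, and the second states when the average is declared missing. Neither says that passing its own test is sufficient. Read together they give one answer for every diary with a defined interval: 4 of 8 entries is missing under the second rule, and 3 of 6 is missing under the first. Two answers arise only if a programmer drops one sentence. What stands is that the joint threshold drifts with visit day, with no stated reason.

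A reader might also take the top of the range as the likely size: 12.0% at 80% completion, or 0.120 × 55 = 6.6 subjects per arm. That needs every subject to attend on Day 115, and it counts all 55 randomized rather than the 44 expected to complete. Assessments after rescue medication are already set to missing under SAP section 5.J, which removes more subjects. Falling between the rules is also not the same as a changed outcome, because only a subject who would otherwise be a responder can change status.

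Finally, the consequences are limited. SAP section 5.A confines formal comparison to the primary endpoint. For the change endpoint, LOCF will usually carry the Week 15 average if that is available, so the mean may move little. These limits are fair and they keep the point minor. They do not explain why the threshold should depend on visit date, and they do not help the group whose interval has no end.

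**Conclusion.** The point holds as a minor defect in a stated rule. The Week 16 interval is 6 to 10 days for subjects who enter follow-up and attend within the visit window. Joint application then requires 4, 4, 5, 6 or 7 entries for visits on Days 111 to 115. A subject seen on schedule with 4 of 8 entries loses the observed value, while 4 of 7 is accepted at baseline and in Weeks 1 to 15. For subjects not in follow-up, the missing-entry rule cannot be evaluated.

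The size depends on two assumptions that are not in the documents: the daily completion rate and independence between days. High completion makes the effect negligible, and lower completion makes it noticeable for the responder endpoints. The primary endpoint, its power and the gatekeeping sequence are unaffected.

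**What to change.** In SAP section 8.A, define Week 16 as Days 106–112 and Week 17 as Days 113–119 for all subjects, whether or not they enter follow-up. This continues the 7-day sequence and removes the open-ended clause. Cap Week 24 at Days 162–168. Replace the two completeness sentences with one: at least 4 of the 7 daily entries.

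A week anchored on the visit, such as the 7 days before it, looks natural but works less well. For a Day 111 visit it covers Days 104–110 and overlaps Week 15 by two days. For a Day 115 visit it covers Days 108–114 and leaves Days 106–107 in no week. If Week 17 then starts on the visit day, its length varies from 5 to 9 days. Subjects without a Week 16 visit would have no anchor.

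The cost is a few lines of SAP wording and a simpler date derivation, with no new data. There are two downsides. Entries on or after Day 113 no longer count toward Week 16. For a visit on Day 112 or Day 111, the week includes one or two days from the visit day onward.

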7.1.2.3. AD Flares and Rescue Treatment

AD is a chronic relapsing skin condition that is characterized by periods of disease flare or escalation of symptoms. Many flare definitions rely on a physician's assessment or subject report (38), however a relatively recent review suggests that an escalation of treatment (or rescue) and days of topical corticosteroid (TCS) use were good indicators of flare and flare duration (39). Therefore, when an AD flare occurs, its onset and duration will be documented as an AE by the location(s) of flare involvement. If the Investigator determines that the flare is severe enough to merit "rescue" treatment, document the choice of TCS and

instructions for its use and the duration of such permitted rescue TCS treatment. The subject need not be discontinued in this situation. Permitted TCS medications to treat AD flares may include the following:

- Cream based preparations or lotion in hair bearing areas
- Low to moderate potency TCS (WHO classification VII-IV) equivalent to class VII – IV according to the U.S classification are allowed. The TCS regimen will be adjusted to the flare activity and tolerability by the subject, and stopped when lesions are cleared.
 - Examples:
 - Methylprednisolone acetate 0.1%
 - Mometasone furoate 0.1%
 - Betamethasone valerate cream 0.1%
- If possible, Investigators should attempt to limit the first step of rescue therapy to permitted TCS rescue treatment and escalate to systemic medications only for patients who do not respond adequately after the treatment of permitted TCS.

If a patient receives any other rescue treatment including other topical rescue treatments (apart from permitted TCS and bland emollients), systemic corticosteroids or nonsteroidal systemic immunosuppressive/immunomodulating drugs (cyclosporine, methotrexate, mycophenolate mofetil, azathioprine, Janus kinase inhibitors, biologic agents, etc), the study treatment will be immediately discontinued. In this situation, subjects should remain in the study and continue with study procedures (complete the schedule of study visits and assessments) but will not receive additional study drug administration.

Investigators should make every attempt to conduct efficacy and safety assessments (eg, disease severity scores, safety labs) immediately before administering any rescue treatment. An unscheduled visit may be used for this purpose if necessary.

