10.5.1.3. Other Efficacy Endpoints

Comparing each CBP-201 regimen to placebo from Baseline to W16:

- Change in POEM

- Number of subjects with AD flares (defined as escalation of therapy evidenced by TCS usage) from Baseline to W8 and from W8 to W16
- Proportion of subjects achieving ≥ 2 -point improvement in IGA from Baseline to W16
- Change in percentage BSA of AD involvement
- Change in SCORAD
- Proportion of subjects achieving ≥ 3 -point reduction in weekly average of PP-NRS
- Proportion of subjects achieving ≥ 4 -point reduction in weekly average of PP-NRS
- Change in DLQI

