- Proportion of subjects achieving ≥ 4 -point reduction in weekly average of PP-NRS from Baseline to Week 16 and Week 20.
- Change in Patient Oriented Eczema Measure (POEM) from Baseline to Week 16 and Week 20.
- Change in percentage body surface area (BSA) of AD involvement from Baseline to Week 16 and Week 20.
- Change in Severity scoring of AD (SCORAD) from Baseline to Week 16 and Week 20.
- Change in Dermatology Life Quality Index (DLQI) from Baseline to Week 16 and Week 20.
- Number of subjects with AD flares from Baseline to Week 8 and from Week 8 to Week 16 and Week 20.
- Number of AD flares (defined as escalation of therapy evidenced by Topical corticosteroids (TCS) usage) from baseline through Week 16.
- Number of days with AD flare through Week 16.

D. Safety Endpoints

- Adverse events (AEs) reported
- Vital Signs (VS)
- Physical examinations

- Injection site changes
- Safety laboratory parameters
- Electrocardiogram (ECG) parameters
- Number (%) of subjects displaying positive anti-drug antibodies (ADA)

4. Study Design

A. Design Overview

This is a phase 2, randomized, double-blind, placebo-controlled study to assess the efficacy, safety, PD and PK profile of CBP-201 administered to eligible adult subjects with moderate to severe AD. The study period includes a treatment period of 16 weeks and a follow-up period of 8 weeks.

Approximately 220 subjects who meet eligibility criteria and consent to participate in the study are randomly assigned in a 1:1:1:1 ratio to one of the following treatment groups:

- CBP-201 1800 mg (150 mg Q2W): CBP-201 600 mg (4 vials) on D1, 1 vial of CBP-201 and 1 vial of placebo on W2 and the same dose Q2W thereafter through W16. Total CBP-201 dose over 16 weeks: 1800 mg.
- CBP-201 3000 mg (300 mg Q2W): CBP-201 600 mg (4 vials) on D1, CBP-201 300 mg (2 vials) on W2 and Q2W thereafter through W16. Total CBP-201 dose over 16 weeks: 3000 mg.
- CBP-201 1800 mg (300 mg Q4W): CBP-201 600 mg (4 vials) on D1, placebo (2 vials) on W2, CBP-201 300 mg (2 vials) on W4, W8, W12 and W16, alternating with placebo (2 vials) on W6, 10, and 14. Total CBP-201 dose over 16 weeks: 1800 mg.
- Placebo: 4 vials on D1, 2 vials on W2 and Q2W thereafter through W16.

B. Study Population

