For binary secondary efficacy endpoints (IGA response, EASI-50, 75, 90 response), counts, percentage, and 95% CIs obtained based on the Clopper-Pearson method (SAS PROC FREQ PROCEDURE, exact binomial) will be presented for each CBP-201 regimen and placebo, respectively, based on FAS; p-value for pairwise comparisons for each CBP-201 group vs. placebo will also be presented in an exploratory manner. For responder endpoints, missing value will be imputed using NRI.

For change from baseline to Week 16 in weekly average PP-NRS, the method for statistical analysis is similar as described above for primary efficacy endpoint, with replacement of PP-NRS by EASI in the model, using LOCF for all visits based on FAS and also WOCF at Week 16 as sensitivity analysis..

Proportion of subjects achieving IGA (0-1), and proportion of subjects achieving EASI-50, EASI-75, or EASI-90 in the EASI score will be plotted by treatment and scheduled visits using bar plots. Mean reduction (\pm SD) from baseline for PP-NRS will be plotted by treatment and study week.

D. Other Efficacy Outcome Analyses

Binary endpoints will be analyzed using similar method as described above for secondary efficacy endpoints:

- EASI-50/EASI-75/EASI-90 at Week 20
- EASI-100 at Week 16 and Week 20
- IGA Score 0
- Proportion of subjects achieving ≥ 2 -point improvement in IGA from Baseline to Week 16

- Proportion of subjects achieving ≥ 3 -point reduction in weekly average of PP-NRS from Baseline to Week 16, defined for the subset of subjects whose baseline NRS is ≥ 3 .
- Proportion of subjects achieving ≥ 4 -point reduction in weekly average of PP-NRS from Baseline to Week 16, defined for the subset of subjects whose baseline NRS is ≥ 4 .

Continuous endpoints will be analyzed using similar method as described above for primary efficacy endpoints, with replacement of each endpoint by EASI in the model; no formal statistical comparison will be performed:

- Change from Baseline to Week 20 in weekly average PP-NRS
- Change in POEM from Baseline to Week 16
- Change in percentage BSA of AD involvement from Baseline to Week 16
- Change in SCORAD from Baseline to Week 16
- Change in DLQI from Baseline to Week 16

AD flares will be recorded as AEs on the eCRF. AD flare related efficacy endpoints will be analyzed using descriptive statistics for each treatment group. Definitions are as follows:

- Number of AD flares from baseline through Week 16

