 - defined as the total number of AD flares with an onset date from baseline to Week 16. Number of AD flares will be summarized using descriptive statistics for each treatment group using OC. Number and percentage (along with the 95% CI) of subjects with at least one AD flare during each period will be provided for each treatment group.
- Number of subjects with AD flares from Baseline to Week 8 and from Week 8 to Week 16 and Week 20:
 - AD flares on Baseline to Week 8 and from Week 8 to Week 16 will be defined similarly by AE onset date as described above. AD flares that start before Week 8 and are ongoing or resolve after Week 8 will be counted in the first period (baseline to Week 8) only.
- Number of days with AD flares through Week 16:
 - the duration of each AD flare is defined as (resolution date of AE – onset date of AE + 1) among subjects with at least one AD flare. For subjects reporting more than one flare, the total subject-days of duration would be calculated and used in statistical summary. Details regarding calculation of duration of AE are described in section 9 below. Number of days with flares will be summarized using descriptive statistics for each treatment group.

All efficacy endpoints will be summarized for FAS using descriptive statistics or frequency counts and percentage for all scheduled visits, for each treatment group.

9. Safety Analyses

Safety analyses will use data from the Safety population. Safety data will be summarized using frequency tables (counts with percentages) and will be presented by treatment and scheduled visits if applicable. Continuous safety data will be summarized using descriptive statistics by treatment and scheduled visits. Data will be compared to the reference ranges provided and be checked for abnormality and/or clinically relevant changes from baseline, where applicable. No formal statistical comparisons will be performed for safety endpoints.

A. Exposure

The following exposure parameters will be defined and summarized by treatment group using descriptive statistics:

- Number and percentage of subjects receiving any injection of study drug at each visit
- Number of injections received at each visit and overall
- Volume (mL) of study drug injected at each visit and overall
- Dose (mg) of study drug injected at each visit and overall
- Number and percent of subjects that have dose interruptions, as well as those with dose interruptions due to AEs

B. Adverse Events

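### SAP 8.D counts AD flares from AE records without the TCS condition in their definition, and sums flare-days without merging overlaps or stopping at Week 16

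*SAP*

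**What the plan says.** **Definition.** SAP 3.C lists "Number of AD flares (defined as escalation of therapy evidenced by Topical corticosteroids (TCS) usage) from baseline through Week 16". Protocol 10.5.1.3 attaches the same condition to a different endpoint: "Number of subjects with AD flares (defined as escalation of therapy evidenced by TCS usage", for the periods before and after Week 8. Neither document attaches it to the number of days with flare.

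**Capture.** Protocol 7.1.2.3 says that when a flare occurs, "its onset and duration will be documented as an AE by the location(s) of flare involvement". TCS comes in only on a further condition: "If the Investigator determines that the flare is severe enough to merit" rescue, the site then records the TCS chosen, the instructions and the duration.

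**Counting.** SAP 8.D states that "AD flares will be recorded as AEs on the eCRF" and then gives its own definitions:

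- The number of flares is "defined as the total number of AD flares with an onset date from baseline to Week 16".
- Subjects with flares are assigned to periods by the same AE onset rule.
- The duration of a flare is the AE resolution date minus the AE onset date, plus 1.
- "For subjects reporting more than one flare, the total subject-days of duration would be calculated and used in statistical summary".

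**Status.** The protocol synopsis lists the number of flares and flare-days as key secondary endpoints. SAP 3.C places all three flare endpoints among the other endpoints, and SAP 8.D analyses them descriptively.

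**The concern.** The protocol's rationale for tying flares to treatment (7.1.2.3) is that escalation of therapy and days of TCS use are good markers of a flare and its length. The rule that would be programmed uses neither. It takes every AE recorded as a flare, treated or not, and measures length by AE dates. A table produced under 8.D would therefore carry a label that does not match its content.

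The flare-day rule has a separate problem. A quantity described as days with flare through Week 16 should not count one calendar day twice or include days after Week 16. The stated rule allows both.

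**Working it through.** The plan gives no flare rate, count or power for these endpoints, so there is no figure to reproduce. The check sets the rules side by side and applies them to worked cases. Record patterns and shares below are assumptions chosen to show how the rules behave.

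**1. Rules compared**

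| Endpoint | TCS condition in the definition | TCS condition in SAP 8.D |
|---|---|---|
| Number of flares | Yes (SAP 3.C) | None |
| Subjects with flares | Yes (Protocol 10.5.1.3) | None |
| Days with flare | Not stated | None; AE dates |

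The only count-once rule, in SAP 9.B, applies to the TEAE incidence summaries and not to these endpoints.

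**2. Untreated flares.** Let u be the share of AE-recorded flares without TCS, with one AE per flare. The 8.D count divided by the count under the definition is 1/(1 − u):

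- u = 0: 1.00
- u = 0.25: 1/0.75 = 1.33
- u = 0.5: 1/0.5 = 2.00

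The number of subjects with flares is also affected, because a subject whose only flares were untreated is counted.

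**3. Days after Week 16.** For a flare on Days 110 to 140, 8.D gives 140 − 110 + 1 = 31 days. By Day 113, 113 − 110 + 1 = 4 have occurred, so 27 lie outside the window. With the ±2-day visit window (Day 111 to 115), 2 to 6 days fall inside.

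**4. Overlapping records.** Two flare records that both run from Day 20 to Day 33 give 14 + 14 = 28 days, against 14 distinct calendar days. Three records of the same 40 days give 3 × 40 = 120 days. That exceeds the 113 days from Day 1 to Day 113, although only 40 calendar days are involved.

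**5. If sites enter one AE per location.** With an average of k records per flare, the same for treated and untreated flares, the count ratio becomes k/(1 − u):

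| k | u = 0 | u = 0.25 | u = 0.5 |
|---|---|---|---|
| 1 | 1.00 | 1.33 | 2.00 |
| 2 | 2.00 | 2.67 | 4.00 |
| 3 | 3.00 | 4.00 | 6.00 |

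The first row applies if each flare is one AE. Neither k nor u is in the documents. The number of subjects with a flare does not depend on k.

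**6. Combined case.** Take a TCS-treated flare on Days 20 to 33 and an untreated one on Days 60 to 69. With one AE per flare, 8.D gives 2 flares and 14 + 10 = 24 days. If the first were entered at three locations, 8.D would give 3 + 1 = 4 flares and 3 × 14 + 10 = 52 days. Requiring TCS and merging overlaps gives 1 flare and 14 calendar days either way.

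**The case against.** A definition in SAP section 3 need not be repeated in section 8 to apply. The visit procedures in Protocol 7.1.3 to 7.1.8 ask sites to document flares that required TCS, and SAP 6.C flags rescue medications, so a programmer might apply the filter anyway. This is a fair reading of the intent. However, 8.D introduces its own definitions, names AE records as the source, and contains neither a TCS condition nor a link between AE and medication records. The visit procedures list TCS-requiring flares separately from AEs, and the SAP does not name that item as the source of the counts.

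A reader might also infer that a flare at several body sites will be counted several times. The documents do not support that. Protocol 7.1.2.3 speaks of a single AE with its location or locations, which fits one record listing several sites as well as one record per site. Protocol 11.1.4 prefers one diagnosis to separate symptoms, and 8.D speaks of flares rather than rows. The eCRF is not available to settle it. Multiple counting is therefore possible but not shown, and its size may be zero.

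Finally, because the TCS condition is not attached to flare-days, no TCS-based day count can be called the documented one. The day-count problem rests on overlap and truncation alone.

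**Conclusion.** The point holds in a limited form. As written, SAP 8.D counts untreated flares in two endpoints that are defined by TCS use. Its flare-day sum can count a day twice or include days after Week 16. The truncation gap needs no assumption about how sites record location; the effect of untreated flares depends on u, which is unknown.

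A reader might infer that the placebo arm is inflated most because its disease is more extensive. Protocol 13.6.2 says only that placebo subjects are expected to need TCS more often or for longer; it says nothing about the number of flare locations. Untreated flares could also blur a TCS-based contrast between arms. The direction of any bias cannot be read from the documents.

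The consequence is limited. SAP 8.D summarizes these endpoints descriptively, and Protocol 13.6.2 plans no formal comparison for secondary endpoints. The primary conclusion is unaffected. The change is still worth making because the protocol ranks flare counts and flare-days as key secondary endpoints.

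**What to change.** Amend SAP 8.D as follows:

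1. Use one flare definition for all three flare endpoints: an AE-recorded flare with a linked rescue-TCS record, drawing on the rescue medications already flagged under SAP 6.C. State the linkage rule, for example by dates and indication.
2. Report all AE-recorded flares, treated or not, as a supplementary summary.
3. Merge flare AE records with overlapping dates within a subject into one episode before counting.
4. Count flare-days as distinct calendar days from Day 1 to the Week 16 visit.
5. State how the analysis classifies a flare that went straight to rescue other than TCS. Protocol 7.1.2.3 asks for TCS first only where possible, so a strict TCS condition would miss such a flare.

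The cost is SAP wording, some programming, and the work of linking AE to medication records. The documents do not show whether an explicit link exists in the eCRF; if not, matching by date will leave some records for blinded review. Merging can also join two distinct flares that overlap in time, which lowers the episode count but not the calendar-day count.
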